4. Plan for Grading Adverse Events:

HIC 2000030749

The following scale will be used in grading the severity of adverse events noted during the study:

1. Mild adverse event
2. Moderate adverse event
3. Severe

Plan for Determining Seriousness of Adverse Events:

Serious Adverse Events:

In addition to grading the adverse event, the PI will determine whether the adverse event meets the criteria for a Serious Adverse Event (SAE). An adverse event is considered serious if it results in any of the following outcomes:

1. Death.
2. A life-threatening experience in-patient hospitalization or prolongation of existing hospitalization.
3. A persistent or significant disability or incapacity.
4. A congenital anomaly or birth defect; OR
5. Any other adverse event that, based upon appropriate medical judgment, may jeopardize the subject's health and may require medical or surgical intervention to prevent one of the other outcomes listed in this definition.

An adverse event may be graded as severe but still not meet the criteria for a Serious Adverse Event. Similarly, an adverse event may be graded as moderate but still meet the criteria for an SAE. It is important for the PI to consider the grade of the event as well as its "seriousness" when determining whether reporting to the IRB is necessary.

6. Plan for reporting UPIRSOs (including Adverse Events) to the IRB

The principal investigator will report the following types of events to the IRB:

Any incident, experience or outcome that meets ALL 3 of the following criteria:

1. Is unexpected (in terms of nature, specificity, severity, or frequency) given (a) the research procedures described in the protocol-related documents, such as the IRB-approved protocol and informed consent document and (b) the characteristics of the subject population being studied; AND

HIC 2000030749

2. Is related or possibly related to participation in the research (possibly related means there is a reasonable possibility that the incident, experience, or outcome may have been caused by the procedures involved in the research); AND
3. Suggests that the research places subjects or others at greater risk of harm (including physical, psychological, economic, legal, or social harm) than was previously known or recognized.

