Unanticipated Problems Involving Risks to Subjects or Others (UPIRSOs) may be medical or non-medical in nature, and include – but are not limited to – serious, unexpected, and related adverse events and unanticipated adverse device effects. Please note that adverse events are reportable to the IRB as UPIRSOs only if they meet all 3 criteria listed above.

These UPIRSOs/SAEs will be reported to the IRB in accordance with IRB Policy 710, using the appropriate forms found on the website. All related events involving risk but not meeting the prompt reporting requirements described in IRB Policy 710 should be reported to the IRB in summary form at the time of continuing review. If appropriate, such summary may be a simple brief statement that events have occurred at the expected frequency and level of severity as previously documented. In lieu of a summary of external events, a current DSMB report can be submitted for research studies that are subject to oversight by a DSMB (or other monitoring entity that is monitoring the study on behalf of an industry sponsor).

7. Plan for reporting adverse events to co-investigators on the study, as appropriate the protocol's research monitor(s), e.g., industrial sponsor, Yale Cancer Center Data and Safety Monitoring Committee (DSMC), Protocol Review Committee (PRC), DSMBs, study sponsors, funding and regulatory agencies, and regulatory and decision-making bodies.

For the current study, the following individuals, funding, and/or regulatory agencies will be notified:

- All Co-Investigators listed on the protocol.
- National Institute of Health

1 Other Data Safety Monitoring Board (DSMB) or Committee (DSMC): The Yale PET Center's internal Data Safety Monitoring Board, composed of the Directors of the PET Center, also meets to review any adverse events on a monthly basis.

1 Yale New-Haven Radiation Safety Committee (if applicable)

Yale University Radiation Safety Committee (if applicable)

The principal investigator [name] [name] will conduct a review of all adverse events upon completion of every study subject. The principal investigator will evaluate the frequency

HIC 2000030749

and severity of the adverse events and determine if modifications to the protocol or consent form are required.

Research staff will call subject 1-3 days after the PET scan to check in and address any adverse events that may have arisen post PET scan.

The study will be stopped if either of the following occur:

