- 1) If 1 or more subjects experiences a serious adverse event (SAE), which is considered by the investigator to be possibly or probably related to the radiotracer.
- 2) If 2 or more subjects experience AEs of severe intensity, which are considered by the investigator to be possibly or probably related to the radiotracer and of clinical concern.

After review of the safety data, SAEs and AEs confirmed to have been related to the radiotracer will be reported to the FDA and the appropriate regulatory committees at Yale. The study will be placed on hold until a determination is made as to whether the study may continue as written, if modifications are needed, or if the study will be discontinued.

Definitions

Adverse event (AE) means any untoward medical occurrence associated with the use of an intervention in humans, whether or not considered intervention-related (21 CFR 312.32 (a)).

An AE or suspected adverse reaction is considered "serious" (SAE) if, in the view of either the investigator or sponsor, it results in any of the following outcomes:

- death,
- a life-threatening adverse event,
- inpatient hospitalization or prolongation of existing hospitalization,
- a persistent or significant incapacity or substantial disruption of the ability to conduct normal life functions,
- a congenital anomaly/birth defect, or
- An important medical event that may not result in death, be life-threatening, or require hospitalization may be considered serious when, based upon appropriate medical judgment, they may jeopardize the participant and may require medical or surgical intervention to prevent one of the outcomes listed in this definition. Examples of such medical events include allergic bronchospasm requiring intensive treatment in an emergency room or at home, blood dyscrasias or convulsions that do not result in inpatient hospitalization, or the development of drug dependency or drug abuse.

HIC 2000030749

Severity

Adverse events will be graded according to [name grading scale, e.g. CTCAE v5.0]. For AEs not included in the protocol defined grading system, the following guidelines will be used to describe severity.

- Mild – Events require minimal or no treatment and do not interfere with the participant's daily activities.
- Moderate – Events result in a low level of inconvenience or concern with the therapeutic measures. Moderate events may cause some interference with functioning.

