7.12 Data Safety Monitoring Plan

The principal investigator [name] [name]. will conduct a review of all adverse events upon completion of every study subject. The principal investigator will evaluate the frequency and severity of the adverse events and determine if modifications to the protocol or consent form are required.

Research staff will call subject 1-3 days after the PET scan to check in and address any adverse events that may have arisen post PET scan.

The study will be stopped if either of the following occur:

1) If 1 or more subjects experiences a serious adverse event (SAE), which is considered by the investigator to be possibly or probably related to the radiotracer.

HIC 2000030749

2) If 2 or more subjects experience AEs of severe intensity, which are considered by the investigator to be possibly or probably related to the radiotracer and of clinical concern.

After review of the safety data, SAEs and AEs confirmed to have been related to the radiotracer will be reported to the FDA and the appropriate regulatory committees at Yale. The study will be placed on hold until a determination is made as to whether the study may continue as written, if modifications are needed, or if the study will be discontinued.

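### Both mandatory stopping rules name only events the investigator calls possibly or probably tracer-related: read literally they omit definite events, and they give the PET Center DSMB no trigger

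*Combined protocol and SAP*

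**What the plan says.** Section 6.2.3 sets two mandatory stops, and 7.12 repeats them.

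- Rule 1: one or more participants with a serious adverse event "which is considered by the investigator to be possibly or probably related to the radiotracer".
- Rule 2: two or more participants with severe adverse events "considered by the investigator to be possibly or probably related to the radiotracer and of clinical concern". Section 7.12 has the same condition: "which are considered by the investigator to be possibly or probably related to the radiotracer and of clinical concern".

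Section 6.2.3 contains two attribution scales. The one under attribution of adverse events runs Definite, Probable, Possible, Unlikely, Unrelated, and the principal investigator applies it. The one under relationship to the investigational product runs Definitely, Probably and Potentially Related, then Unlikely and Not Related, and the examining clinician applies it.

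There are two layers of review. The principal investigator "will conduct a review of all adverse events upon completion of every study subject". The PET Center's internal DSMB, "composed of the Directors of the PET Center, also meets to review any adverse events on a monthly basis".

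For adverse events, 6.2.3 says that "the following individuals, funding, and/or regulatory agencies will be notified", and lists the co-investigators, NIH, the DSMB and, where applicable, two radiation safety committees. No relatedness condition is attached to that list.

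Three passages say who may stop or suspend the study at discretion. Section 6.2.3 names the principal investigator, the HIC and the RSC. Section 6.5.4 adds NIH (NIDA). Section 7.11 has the principal investigator, the HIC, NIH (NIDA) and the RIDC. None names the DSMB.

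After the rules, both 6.2.3 and 7.12 say that events confirmed as tracer-related go to the FDA and Yale committees, and that the study is held pending a determination. Neither says who does the confirming.

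**The concern.** A mandatory stopping rule should cover its clearest case on its face. These two name the middle categories of relatedness and skip the top one.

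The second matter is who can trigger them. A board already reads the events every month, but the protocol attaches no consequence to what it concludes. That matters in one situation only: the board thinks an event is due to the tracer, the investigator does not, and the disagreement persists. The stop then moves from mandatory to discretionary, and tracer injections may continue meanwhile. Participants are in good general health, have no direct benefit (3.2.2), and accept a risk that 6.2.3 classes as greater than minimal. An unnecessary hold therefore costs study time and withholds treatment from nobody.

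**Working it through.** The plan gives no operating characteristic for these rules, so there is no figure to reproduce. The check is to run cases through the literal wording.

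| Case | Investigator's view | DSMB's view | Rule fires as written? | After the fix? |
|---|---|---|---|---|
| 1 SAE | possible or probable | any | Yes (rule 1) | Yes |
| 1 SAE | definite | any | No, read literally | Yes |
| 1 SAE | unlikely | probable | No | Yes |
| Severe AEs of clinical concern in 2 participants | definite | any | No, read literally | Yes |
| Severe AEs of clinical concern in 2 participants | unlikely | probable | No | Yes |
| 1 SAE | unlikely, later changed to possible | any | Yes, once changed | Yes |

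The last row limits the point. The rules set no deadline, so an investigator who changes view after hearing the board does trigger the stop. Only persistent disagreement is left uncovered.

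**Counts.**
- Mandatory rules resting on the investigator's view alone: 2 of 2, in both places they are stated.
- Related categories named by the rules: 2 of 3 on each scale, taking Potentially Related as possible.
- Stop-authority lists naming the DSMB: 0 of 3.

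**The hold sentence.** Could it be a third, independent stop that the board could set off? If it stood alone, any confirmed related event, even a mild one, would force a hold. Rule 2's threshold of two participants with severe events would then do nothing. It reads better as the step after a rule has fired.

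**Routes left when neither rule fires.**
- NIH is notified without a relatedness condition and may stop the study under 6.5.4 and 7.11, though 6.2.3 omits it.
- The radiation safety committees are notified where applicable, again without a relatedness condition. The RSC may stop under 6.2.3 and 6.5.4, the RIDC under 7.11.
- The HIC (taken here to be the IRB) may stop under all three lists. Prompt reporting to the IRB is made by the principal investigator and requires, among three criteria, that the event "Is related or possibly related to participation in the research". The continuing-review summary likewise covers related events. IRB Policy 710 is not in the documents.
- Section 7.14 also allows termination for unacceptable risk.

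All of these are discretionary.

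**Exposure while a disagreement lasts.** Inputs: 40 participants (5.3.1), 2 injections each (3.2.1), study dates 07/01/2021 to 06/30/2025, which is 48 months (5.1.1).
- Planned injections: 40 × 2 = 80.
- Spread evenly over the study: 80 / 48 = 1.7 a month.
- If all scanning fell in 24 months (assumption): 80 / 24 = 3.3 a month.
- Section 6.2.3 elsewhere mentions up to 3 injections. At 40 × 3 = 120 the figures are 120 / 48 = 2.5 and 120 / 24 = 5.0 a month.

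On the two-scan design, each month of unresolved disagreement means about 2 to 3 further injections on average, before any repeat of a failed scan.

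**The case against.** The strongest reply is that the plan is already cautious. One possibly related serious event is enough to stop. Section 6.2.3 says that the study product is always to be treated as suspect, and a Not Related call needs a documented alternative cause. Adverse effects of the radiopharmaceuticals have not been reported (3.2.1). All of this stands and limits the weight of the point.

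No passage says that the DSMB judges relatedness; it is said only to review events. Its charter is not in the documents. This also stands: the disagreement is a possibility that the monthly review creates, not something the plan describes.

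The omission of definite is very likely editorial, since anyone applying the rule would treat a definite event as at least probable. That is true, but it is a reason to correct the words, not to leave them.

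Three stronger readings are tempting, and the documents support none of them.

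- A reader might infer that nobody can stop the study over the investigator's objection. The three lists say otherwise, and NIH and, where applicable, the radiation committees hear of events whatever their attribution. The IRB criterion is also broader than the rules: it asks about a reasonable possibility of causation by any research procedure, not only the tracer.
- A reader might infer an inconsistency with seriousness, because one definition in 6.2.3 allows a view from the investigator or the sponsor. The same section also assigns the seriousness determination to the principal investigator, so the contrast does not hold.
- A reader might infer one fixed assessor. The second scale gives relatedness to the examining clinician, who need not be the principal investigator. Either way, it is not the board.

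**Conclusion.** The point holds in a narrow form. On the wording alone, the omission of definite events from two mandatory safety rules, in both places they appear, is wrong as written, though probably a slip.

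The missing DSMB trigger is a cheap improvement and not a fundamental flaw. It matters only if the board and the investigator disagree and stay in disagreement, and even then discretionary routes remain. The number of such events cannot be derived from the documents and is expected to be small. If one occurred, the cost of delay would be about 2 to 3 injections a month, assuming two scans per participant and even scanning over 48 or 24 months.

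The conclusion rests on two readings: that the hold sentence follows a fired rule, and that the HIC is the IRB.

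**What to change.** In 6.2.3 and 7.12, reword the attribution clause of both rules to: *considered by the investigator or the PET Center DSMB to be at least possibly related (possible/potential, probable or definite) to the radiotracer*. Keep both thresholds and the investigator's immediate trigger. Rule 2 keeps its clinical-concern condition, judged by whichever of the two makes the attribution. State that the DSMB may add a trigger but not remove one, at its existing monthly review.

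Use one stop-authority list in 6.2.3, 6.5.4 and 7.11, and include the DSMB. This would also settle whether NIH belongs in 6.2.3, whether the radiation body is the RSC or the RIDC, and why NIDA is named when 7.17 gives NIDDK as the funder.

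The cost is a short amendment, with no new body, meeting or staff. The downside is an occasional hold that the investigator alone would not have called. The board consists of the PET Center Directors and the tracer is prepared at that center (6.1.1), so this adds a second view and not full independence. That the board would accept the role is an assumption. If it would not, adding definite to both rules should still be done.

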6.2.4 Pharmacokinetics (if applicable)

N/A

6.2.5 Biomarkers (if applicable)

N/A

6.3 Study Procedures

Visit 1 - Screening procedures:

Potential subjects will complete pre-screening over the telephone for approximately 10 minutes to determine preliminary eligibility based on inclusion/exclusion criteria and basic socio-demographic information will be collected. Potentially qualifying participants will then be screened in person at the Yale New Haven Hospital (YNHH) Research Unit (HRU) with vital signs, EKG, and a medical history and physical exam. Fasting blood will be collected for HbA1C, creatinine, liver enzymes (ALT, AST), TSH, hematocrit, and lipid panel. A urine pregnancy test will be administered.

Oral glucose tolerance test (OGTT) will be administered as follows: Following a 10-hour overnight fast, a nurse will insert an intravenous (IV) catheter. Subsequently, subjects will ingest 7.5 oz of Glucola, which contains 75 g of dextrose in orange flavored water. Blood samples will be taken at -15, 0, 10, 20, 30, 60, 90 and 120 minutes (after glucola ingestion) for the measurement of plasma glucose, insulin, and C-peptide concentrations, and calculation of measurements of insulin sensitivity index (Matsuda Index). Approximately 40 mL of blood will be drawn at this visit.

Body Composition, Percent Body Fat & Percent Body Water: will be assessed using bioelectrical impedance analysis Tanita® scale (FDA cleared); which is a special multi frequency seg-mental body composition analyzer that delivers a very mild electrical current

HIC 2000030749

that allows measurement of fat mass, percent body fat, fat free mass, total body water, and percent body water. This test will be performed at screening visit. For better accuracy, measurement of percent fat and percent body water will be obtained with whole body Dual X-Ray Absorptiometry (DXA) scan (Hologic®) (located in the HRU) on screening-OGTT visit. The scanner arm will move over the participant's body from feet to head. The machine uses a small amount of radiation (one tenth of the amount of radiation from a chest x-ray) to measure body fat, muscle and bone density.

Visit 2 – Whole body PET/CT Imaging Visit - FASTING:

After 2 weeks from visit 1, -participants who qualified for the study will be asked to come to the PET Center to undergo the whole body [11C]MRB PET scan. Participants will be asked to maintain their regular exercise routine.

Human PET-CT Protocol: [11C]MRB will be synthesized at the Yale PET center based on procedures described and previously performed 1,2. An intravenous bolus dose of MRB (~120mCi) will be injected by an infusion pump. PET data will be acquired dynamically for 120 min using the Siemens mCT-X whole-body PET/CT scanner using continuous bed motion to image perform multiple PET bed acquisitions from the top of the head to the lower abdominal region. A CT scan will be performed for attenuation correction and to help delineate the BAT and other regions of interest (ROIs). Images will be reconstructed with an ordered subset expectation maximization algorithm using point spread function correction and time-of-flight information. To delineate fat (WAT, BAT) and skeletal muscle regions of interests (ROIs), CT images are first resliced to match the resolution and location of PET images. As performed in previous studies 2, a supraclavicular ROI is first manually drawn on the CT images. Within that area, the fat ROI is segmented using the CT images and an intensity window from -200 to -50 HU. Subsequently the fat ROI is segmented into WAT and BAT ROIs by using the 11C-MRB PET images: Standardized Uptake Value (SUV) ≥ 1.25 for BAT, SUV < 1.25 for WAT.

Brain ROIs for predetermined NET-rich areas of the brain, including the locus ceruleus, raphe, thalamus and hypothalamus were defined in template space and are applied to the PET images by using the participant's MR image as an intermediate step. For analysis of tracer uptake, mean SUV will be reported for segmentation of adipose tissue. Because the distribution volume ratio (DVR) is a more precise measurement of uptake for reversible tracers 3 such as 11C-MRB, regional quantification of 11C-MRB uptake as DVR (VT/ VND), estimated via multilinear reference tissue model 2 (MRTM2) 4,5 ($t^*=30$ min) using the occipital cortex, a region with low NET density 2,5,6 as the reference region. MRTM2 reduces the variability of MRTM (4) parameter estimates by fixing one of the three parameters, the parameter $k2'$, which is only related to the reference region time-activity curve, to a common value for all target regions. In this study, the parameter $k2'$ was fixed to 0.021 min-1, based on previous brain studies and previous BAT PET studies 2. In addition to

HIC 2000030749

DVR, MRTM2 can estimate R1, the relative radioligand delivery, using a 1 tissue compartment model (1TC). For the 1TC model, volume of distribution, $VT = K1/k2$, where $K1$ (mL/min-1/mL-1) is the rate constant of radiotracer from plasma to tissue of target organ and $k2$ is the rate constant from tissue to plasma. Using a reference region with non-displaceable binding (e.g. occipital lobe) we can estimate similar rate constants: $VND = K'1/k'2$. Recalling that $K1$ and $K'1$ are the rate constants for transfer from plasma to the tissue and reference region, respectively, then we can estimate relative radioligand delivery as $R1 = K1/K'1$.

Visit 3 – Whole body PET/CT Imaging Visit - High-Carbohydrate Mixed Meal Test (MMT)

High Carbohydrate Mixed meal test (MMT):

After 2 weeks from visit 2, participants will come to the PET Center after a 10-hour overnight fast. A nurse will insert an intravenous (IV) catheter and subjects will ingest a liquid meal (65% CHO, 20% fat, and 15% protein, equal to 40% of daily energy expenditure, per ~16 ounces) to be prepared by the Metabolic Kitchen located at the HRU. Blood samples will be collected at -10, 0, 15, 30, 60, 90, and 120 min for measurement of glucose, insulin and C-peptide concentrations 7. Plasma samples will be drawn at baseline and throughout the MMT for measurement of additional hormones (such as leptin, ghrelin, thyroid hormones, and catecholamines) and free fatty acids (FFA) levels. Insulin and glucose will be used to calculate indexes of insulin sensitivity 7-9. Hormones, glucose and FFA will be correlated with PET measurements of brown fat at baseline and during the MMT. Approximately 60 mL of blood will be drawn at this visit.

Participants will undergo whole body [11C]MRB PET scan as described in visit 3. After the MMT, PET data will be acquired dynamically for 120 min using the Siemens mCT-X whole-body PET/CT scanner after an intravenous bolus dose of MRB (~20mCi).

The order of the PET scan visits 2 and 3 will be randomized.

Measurement of Energy Intake: Hunger and fullness will be determined immediately before, during and after the PET scans with Visual Analog Scales (VAS).

Visit 4 – Sympathetic Nervous System Activity (SNSA) measurement Visit - Fasting

After 2 weeks from visit 3, participants will be asked to return for a separated visit for measurements of SNS activity at rest and fasting. This visit will be performed at the Pierce Laboratory ([name] laboratory). The participants will come in the morning (~9am) and will be asked to fast for 10-hour and to maintain their regular exercise routine. The following measurements will be obtained: MSNA, heart rate (HR), blood pressure (BP), electrocardiogram (EKG), and heart rate variability,. The proposed procedures will be performed at fasting (baseline). Participants will be asked to maintain their regular exercise routine.

HIC 2000030749

Muscle sympathetic nerve activity (MSNA): Microneurography is the gold standard, most sensitive and reliable MSNA assessment in humans. The primary measure of sympathetic nervous system activity is peripheral nerve activity, as measured by MSNA.

Muscle sympathetic nerve activity will be quantified by identification and measurement of sympathetic bursts in the integrated neurogram and expressed as burst frequency (number of bursts per unit time). ECG surface electrodes are applied to the chest, an elastic band incorporating a strain gauge element is strapped around the thorax for recording respiratory movements, and a sensor cuff of a servopulse-plethysmography arterial pressure monitor (FINAPRES, Ohmeda) is placed on the middle phalanx of the long finger (held at heart level). The experiments are carried out in an environmentally controlled chamber at an ambient temperature of 27.0 ± 0.1 °C. The experiment will begin with a 60-minute control period. During such time the subjects rest in the reclined position.

Measurements of HR, BP, and EKG (beat-to-beat) will also be obtained during the procedure. An intravenous catheter will be inserted into a forearm vein for blood sampling. Following the instrumentation period, resting HR, pulse interval (PI), BP, and MSNA will be recorded for 10 minutes. Following these measurements, plasma will be taken for measurements of insulin, glucose, free fatty acids, norepinephrine, and epinephrine levels. Approximately 20 mL of blood will be drawn at this visit. After the first blood sample and the 10-min rest phase, subjects will begin a seven-minute period of rest with paced breathing (12 breaths per minute) while HR, BP, PI and MSNA are measured. The subjects will synchronize breathing to a metronome set to a cadence of ~12 breaths per minute (0.2 Hz).

Procedure: Microneurography Recording of multiunit postganglionic muscle sympathetic nerve activity (MSNA) will be made from the common peroneal nerve as it winds around the fibular head with the subject in the supine position with the subject's thigh comfortably supported. This procedure requires us to first trace the course of the nerve using small electrical stimuli applied to the surface of the skin over the nerve or use the ultrasound to visually assist. This allows the microneurographer to find and focus the recording electrode tip on a nerve fascicle associated with muscle sympathetic activity. The time required to focus the electrode on the nerve averages about 30 min and will not exceed 60 min. In optimal conditions the track of the nerve from superficial stimulation is accurate and the nerve remains in position during insertion. An uninsulated subcutaneous electrode will serve as the reference. Mechanoreceptor afferent activity can be recorded during light tapping on the muscle belly or passive muscle stretch. A suitable intrafascicular recording site for MSNA consists of regular bursts and synchronous with the cardiac cycle. The neural activity is amplified (2x104), filtered (0.5-5.0 kHz), rectified, and integrated. The amplified and filtered nerve signal is also led to an audio monitor and through a resistance capacitance circuit (time constant 100 ms). The integrated nerve signal is digitized at 400 Hz along with the ECG signal while respiratory and arterial pressure signals are also sampled at 400 Hz (MacLab 8s). Data for analysis is selected from periods of quiet breathing in which subjects were relaxed and not talking. Microneurography was approved under HIC protocols # 8079, #0512000875, #1609018353 and is currently used under # 2000020950.

HIC 2000030749

Cardiovascular variables. Recorded with a 16-channel computerized data-acquisition system at a sampling Speed of 400 Hz (ADI Instruments PowerLab 9, Castle Hill, Australia). Beat-to-beat DBP, SBP and pulse interval (PI) are determined using peak detection algorithms (44). Brachial artery BP and HR are measured with an automated sphygmomanometer (Colin Medical Instruments Corp, Komaki, Japan). Heart rate and pulse interval will be determined beat-to-beat from lead II of the EKG recording.

Visit 5 – Sympathetic Nervous System Activity (SNSA) measurement Visit – Mixed Meal Test (MMT)

After 2 weeks from visit 4, participants will be asked to return for a separated visit for measurements of SNS activity at rest and after intake of liquid meal. Participants will undergo similar procedures described on visit 4. However, MSNA will be obtained after MMT. The participants will come in the morning (~9am) and will be asked to fast for 10-hour and to maintain their regular exercise routine. A nurse will insert an intravenous (IV) catheter and subjects will ingest a liquid meal (65% CHO, 20% fat, and 15% protein, equal to 40% of daily energy expenditure, per ~16 ounces) to be prepared by the Metabolic Kitchen. Measurements of HR, BP, and EKG (beat-to-beat) will be obtained during the procedure. An intravenous catheter will be inserted into a forearm vein for blood sampling. Following the instrumentation period, resting HR, pulse interval (PI), BP, and MSNA will be recorded for 10 minutes. Following these measurements, plasma will be taken for measurements of insulin, glucose, free fatty acids, norepinephrine, and epinephrine levels. Approximately 40 mL of blood will be drawn at this visit.

Participants will be asked to maintain their regular exercise routine. The order of SNSA Fasting and MMT visits (visits 4 and 5) will be randomized. All study visits will be conducted within an 8-week period (including the two PET and SNSA scans).

